#### Mothers: at delivery.

A second blood (20 ml), urine and stool sample will be obtained at delivery, before the mother leaves hospital. The blood samples will be used to perform a full blood count (for assessment of post-partum anaemia) a malaria slide and studies of the maternal immune response. The urine sample will be used as part of the assessment of pre-eclampsia and eclampsia. The stool sample will be used to determine the presence of persisting helminth infections, and to guide treatment in the case of *Strongyloides*. A placental smear will also be examined for malaria. Mothers found to have malaria will be treated.

After delivery, participants will be taken home if possible, to ensure follow up.

Mothers who receive the study drugs but do not deliver the baby in the hospital will be followed up at home to determine the outcome of the pregnancy.

#### Mothers: treatment of helminths post delivery.

All mothers will receive mass treatment with albendazole 400 mg and praziquantel 40 mg/kg; both drugs will be given as a single stat dose. Mothers found to have *Strongyloides* will be treated with albendazole 400 mg daily for three days. This treatment will be provided when the mother attends the follow up clinic with her baby six weeks after delivery, by which time both her stool results will be available.

Protocol amendment, March 2003. "Effect of praziquantel treatment during pregnancy on antischistosome immune responses in pregnant women and their infants." Mothers who have schistosomiasis will be asked to provide an additional blood sample (maximum volume 30 ml) before this post-delivery treatment, and a further follow-up stool and blood sample (maximum volume 30 ml) a further six weeks later. These samples will allow a comparison of both the immunological and the therapeutic effects of treating schistosomiasis in pregnancy, with the effects of treatment after delivery.

Children: at delivery.

For children, cord blood will be obtained at delivery.

#### Children: follow up visits.

A clinic at which mothers and children can be seen for follow up will be established in the renovated building at the Private Wing. Children will be seen there at scheduled follow up visits, or if they are sick.

Children will be seen routinely at their immunisation visits (6, 10 and 14 weeks) and then every three months up to the age of 18 months. This will allow their immunisations to be documented (at 6, 10 and 14 weeks, and then measles immunisation at 9 months) and their weight to be recorded. At first this will be done at the study clinic. Later it may be possible to devolve some of these visits to community clinics nearer to the mothers' homes. At one year mothers will be asked to give informed consent on behalf of the children for participation in the randomised, placebo controlled trial of three-monthly albendazole treatment. At 15 and 18 months they will receive their first two doses of albendazole or placebo. At 18 months blood samples will be obtained from children of HIV-positive mothers to ascertain the child's HIV status.

At routine annual follow up visits clinical data, blood for full blood count, malaria slide and immunological studies (2-5 ml) and stool samples will be obtained. Children found to have helminths in stool samples collected at annual visits will be treated by the field workers.

Protocol amendment, January 2009. At five years, 10 ml will be obtained to accommodate assessment of TB infection by T-spot.TB® assay and assessment of additional immune responses in children who were exposed to schistosomiasis in utero. At six years, 5 ml will be obtained for a T-spot.TB® assay.

Protocol amendment, January 2009. For more detailed assessment of schistosomiasis infection at the age of five years in children who were exposed to schistosomiasis in utero, three stool samples will be obtained from this subgroup of five year olds.

#### Children: interim disease events.

To obtain information about disease events, participants will be visited every two weeks by a field worker based in their Local Council area. Each field worker will be equipped with a bicycle, a thermometer and equipment to prepare malaria slides. The child's temperature will be recorded at each visit. Episodes of cough, diarrhoea or fever, and medication, immunisations or clinic visits in the preceding period, will be noted. Two malaria slides will be prepared for any child who is febrile ( $\geq 37.5$  °C). One will be brought by the mother to the clinic to be used for clinical purposes. The other will be kept by the field worker for later processing and analysis. Participants will be asked to attend the study clinic for any severe illness. Out of clinic hours they will be asked to attend the General Hospital.

#### Diagnosis of HIV infection.

- For mothers who wish to know their HIV status, two different rapid HIV tests will be performed in the antenatal clinic. Samples positive on both tests will be considered positive. Samples negative on both tests will be considered negative. Mothers will be informed accordingly. Samples with discrepant results will be sent to UVRI for further tests in [name] laboratory. These mothers will be given an appointment in 2 weeks to come for their results.
- For mothers who do not wish to receive their results, the same procedures will be followed but the rapid tests will be performed in our laboratory at UVRI.
- Quality assurance will be provided by the MRC serology laboratory. All of the first 100 samples (positive or negative), and all of the first 100 positive samples, tested in the programme will be tested in parallel. If the results show good agreement we will then send the first 10 samples each month, plus all samples which show discordant results on the two initial rapid tests, for quality assurance. These follow-up quality control samples will be submitted for analysis every quarter.

#### Diagnosis of syphilis.

- A rapid RPR test will be conducted in the clinic. Samples which are positive on RPR will be further examined using a rapid TPHA test. Mothers will be treated for syphilis if both the RPR and TPHA are positive. These mothers will also be asked to send their partners for treatment.
- Quality assurance for the RPR will be provided by the MRC serology laboratory. All of the first 100 samples tested in the programme will be tested in parallel. If the results show good agreement we will then send the first 10 samples each month for quality assurance. These follow-up quality control samples will be submitted for analysis every quarter.

#### Parasitology

• Stools will be examined by the Kato-Katz method for helminth ova, and by concentration for larvae.

- Serum will be examined for *Schistosoma* circulating anodic antigen (CAA) in HIV-infected women and their children, in whom stool examination is insensitive.
- Urine examination for *S. haematobium* will not be conducted as the prevalence is low in this area. None of 100 samples examined for S. haematobium in a previous study among HIV-positive adults was positive ([name], unpublished data).
- The prevalence of *Mansonella* infection has been found to be about 8% among HIV-positive adults in Entebbe using a modification of Knott's method. However, none of 50 samples tested for *Wuchereria bancrofti* antigen were positive (ICT Filariasis, Amrad ICT, Frenchs Forest NSW, Australia) ([name], unpublished data). The modified Knott's method will therefore be used to examine samples of maternal blood for *Mansonella*.
- Thick blood films and placental smears will be examined for malaria.
- External quality assurance for the Kato-Katz method will be contributed by the Vector Control Programme. The laboratory subscribes to the American College of Pathologists for quality assurance for general parasitology.

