- The delay in treating mothers randomised to treatment after delivery would be, at most, just over 7 months, since mothers would not be treated in the first trimester in any case. There appears to be no evidence that progression of disease caused by schistosomiasis is any faster in pregnant women than in other adults. Persistent diarrhoea with blood is considered to be the pathological effect of chronic schistosomiasis most likely to show an immediate response to treatment, so we have planned to exclude women with these symptoms from the study, investigate them, and treat them if schistosomiasis is found. Otherwise, chronic schistosomiasis, including hepatosplenic schistosomiasis, is frequently asymptomatic, or the symptoms are non-specific and often ignored. The severe sequelae of long-term, heavy infection, such as portal hypertension and oesophageal varices, are unlikely to be much affected by a delay in treatment of, at most, just over 6 months. Therefore, as far as we know, the delay in treatment in some mothers is unlikely to have serious adverse consequences for their health.
- The prevalence of schistosomiasis in the pilot study (>20%) would justify a mass treatment approach if treatment in pregnancy were found to be specifically beneficial to the mother or child. In addition, examination of the single stool sample obtained may detect only about 60% of infected mothers. Therefore we have proposed to study a mass treatment intervention in pregnancy rather than to use selective treatment.

Advice has been given by colleagues at the Ministry of Health, and Uganda Virus Research Institute (UVRI).

Protocol amendment, January 2009. The following additional ethical considerations relate to the introduction T-spot.TB® testing for TB infection among five and six year olds, and to the use of stored samples for investigation of herpesviruse infections.

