#### **CHILDREN**

At One Year Follow-Up Children will be randomised to receive routine albendazole every 3 months or placebo, starting at 15 months. All will receive annual selective treatment based on stool examination.						
Group C1	Group C2					
Albendazole every 3 months and annual	Placebo every 3 months and annual					
selective treatment.	selective treatment.					

Annual Follow-Up Visits to Age 5 Years	
Helminths present, treated	Helminths absent

The analysis for the effect of maternal intestinal nematode infection will compare groups according to the presence or absence of intestinal nematodes at the antenatal visit, and whether or not they were treated; i.e. outcomes will be compared for children of mothers in groups G1-2-5-6 (intestinal nematodes, treated), G3-4-7-8 (intestinal nematodes, not treated), G9-10-13-14 (no intestinal nematodes, treated) G11-12-15-16 (no intestinal nematodes, not treated). The findings will be adjusted for the presence or absence of schistosomiasis, treatment with praziquantel, and the presence or absence of helminths at delivery. The overall effect of albendazole treatment during pregnancy will be determined by comparing G1-2-5-6-9-10-13-14 vs G3-4-7-8-11-12-15-16.

[figure not shown]
The analysis for the effect of maternal schistosomiasis will compare groups according to the presence or absence of schistosomiasis at the antenatal visit, and whether or not they were treated; i.e. outcomes will be compared for children of mothers in groups G1-3-9-11 (schistosomiasis, treated), G2-4-10-12 (schistosomiasis, not treated), G5-7-13-15 (no schistosomiasis, treated) G6-8-14-16 (no schistosomiasis, not treated). The findings will be adjusted for the presence or absence of intestinal nematodes, treatment with albendazole, and the presence or absence of helminths at delivery. The overall effect of praziquantel treatment during pregnancy will be determined by comparing G1-3-5-7-9-11-13-15 vs G2-4-6-8-10-12-14-16.

The analysis for the effect of intestinal nematodes in children will compare groups according to whether they receive routine albendazole every 3 months or annual selective treatment; i.e. outcomes for children in groups C1 and C2 will be compared. The presence or absence of helminths at annual follow up visits will be taken into account.

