#### Clinical

mother's height mother's weight at first visit duration of gestation at first visit mother's gravidity past obstetric history alcohol smoking mother's general health (nutrition, diabetes etc) medicines taken during pregnancy illnesses for which medicines taken maternal syphilis maternal HIV

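### Testing for maternal schistosomiasis differs by HIV status, and the Appendix 4 adjustment list for the infected-versus-uninfected comparison omits maternal HIV

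*Protocol*

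**What the plan says.** **Testing.** The Parasitology section applies one method to every stool: "Stools will be examined by the Kato-Katz method for helminth ova", with concentration for larvae. For schistosomiasis it adds a serum test for "circulating anodic antigen (CAA) in HIV-infected women and their children, in whom stool examination is insensitive". No serum antigen test is stated for HIV-negative women.

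**Stool sensitivity.** In the Ethical Considerations, the case for mass rather than selective praziquantel rests partly on the statement that "examination of the single stool sample obtained may detect only about 60% of infected mothers". It is made about mothers in general.

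**Analysis.** Appendix 4 (Plan for Analysis) says the maternal schistosomiasis analysis will "compare groups according to the presence or absence of schistosomiasis at the antenatal visit, and whether or not they were treated". It does not say which test result makes a woman positive. Findings are to be "adjusted for the presence or absence of intestinal nematodes, treatment with albendazole, and the presence or absence of helminths at delivery". Maternal HIV is not on that list.

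**HIV elsewhere.** Appendix 7 does name it ("maternal syphilis maternal HIV") among potential confounders for birth outcomes, and carries that list over to maternal outcomes. It does not cover the child outcomes in Appendix 4.

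**Nested work.** The March 2003 amendment also selects women by infection status: "Mothers who have schistosomiasis will be asked to provide an additional blood sample".

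**The concern.** The work-up for one exposure depends on HIV status, and HIV status is itself likely to be related to the infants' immune responses and childhood infections. The reason given for limiting the antigen test, poor stool sensitivity in HIV-infected women, sits uneasily with the protocol's own view that one stool misses many infections in all mothers.

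If an antigen-positive, stool-negative woman is labelled infected, the chance that a true infection is labelled differs between HIV-positive and HIV-negative mothers. The two groups compared in Appendix 4 would then differ in HIV mix because of the testing. Without HIV in the adjustment, part of any HIV effect could be read as an effect of maternal schistosomiasis. That contrast is a stated part of Aim 2 and bears on Hypotheses 1 and 2.

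**Working it through.** **1. The plan's own figure.** Appendix 2B expects 12% *S. mansoni* prevalence in 2250 HIV-negative and 250 HIV-positive women: 0.12 × 2250 = 270 and 0.12 × 250 = 30. Both reproduce. The HIV-positive share of the infected is 30/300 = 10%, the same as 250/2500 in the cohort.

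**2. Inputs not in the protocol.** It gives neither stool sensitivity nor combined stool-plus-antigen sensitivity (S) in HIV-positive women. I assume that antigen results count towards the label, that true prevalence is equal by HIV status, that stool sensitivity is 60% in HIV-negative women, and that specificity is perfect. S is varied from 40% to 100%.

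**3. HIV share of the labelled-infected group.** True prevalence cancels:

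share = 250·S / (250·S + 2250 × 0.60) = 250·S / (250·S + 1350)

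| S | Calculation | HIV share |
|---|---|---|
| 40% | 100/1450 | 6.9% |
| 50% | 125/1475 | 8.5% |
| 60% | 150/1500 | 10.0% |
| 80% | 200/1550 | 12.9% |
| 100% | 250/1600 | 15.6% |

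The label is unrelated to HIV only at S = 60%.

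**4. Odds ratio of HIV with the label, no true association.** Taking 12% as the stool-detected figure, true prevalence is 0.12/0.60 = 20%. HIV-negative women: 270 labelled positive, 1980 negative.
- S = 40%: HIV-positive women split 20/230; OR = (20 × 1980)/(270 × 230) = 0.64.
- S = 100%: split 50/200; OR = (50 × 1980)/(270 × 200) = 1.83.

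With 20% detected by stool (the Ethical Considerations give a pilot prevalence above 20%), true prevalence is 33.3% and HIV-negative women split 450/1800. At S = 100%, HIV-positive women split 83.3/166.7, and OR = (83.3 × 1800)/(450 × 166.7) = 2.0.

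**5. How much the antigen test must add.** If stool and antigen errors are independent, S = 1 − (1 − s)(1 − c), where s is stool and c antigen sensitivity in HIV-positive women. For S = 0.60, c = 1 − 0.40/(1 − s): 20% if s = 50%, 33% if s = 40%, 43% if s = 30%. Below these values HIV-positive women are under-represented; above them, over-represented.

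**6. Outcome scale.** Suppose maternal HIV doubles an outcome's risk (an assumption) and schistosomiasis has no effect. The spurious risk ratio is (1 + HIV share in positives)/(1 + HIV share in negatives). At 12% detected:
- S = 40%: share in negatives 230/2210 = 10.4%; ratio 1.069/1.104 = 0.97.
- S = 100%: share in negatives 200/2180 = 9.2%; ratio 1.156/1.092 = 1.06.

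If HIV triples the risk, the ratios are 1.138/1.208 = 0.94 and 1.312/1.184 = 1.11.

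**The case against.** A reader might infer that HIV-positive women are over-represented in the schistosomiasis strata by design. The documents do not support that. No section says that the antigen result defines the strata. The stated reason for the test is that stool performs worse in HIV-infected women, so it may only make up a deficit, or not all of it. Over-representation needs S above stool sensitivity in the other mothers, and S is not given.

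Nor can the preliminary data settle the direction. Appendix 1 found *S. mansoni* in 28 of 93 HIV-positive adults (30%), with the antigen test also used, against 12% by stool only in Appendix 2B. Those samples differ in more than the test.

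The 60% figure is itself soft. It is hedged in the text, and one of its two references is listed as a screening study in HIV-infected people. If stool finds more in HIV-negative women, the neutral point moves. At an assumed 80%, the share is 100/(100 + 1800) = 5.3% for S = 40% and 250/(250 + 1800) = 12.2% for S = 100%. The difference in testing remains, and the direction stays open.

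The objection on scope also stands. Women are randomised before stool results are known. The overall albendazole and praziquantel comparisons do not use infection status. Treated and untreated women within a stratum are balanced on HIV in expectation, because status comes from antenatal samples taken before treatment. Outcomes assessed only in children of HIV-positive mothers (immune responses to HIV, vertical transmission) cannot be confounded by HIV mix.

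Finally, an operational definition of infection may properly sit in a statistical analysis plan. That answers the unstated rule, but not the adjustment list, which Appendix 4 sets out and from which HIV is absent.

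**Conclusion.** The point holds in a limited form. Ascertainment of maternal schistosomiasis differs by HIV status, and the adjustment list for that analysis leaves out maternal HIV. If antigen results count, HIV is a testing-made correlate of the label except at one value of S. Under the assumptions in the working, the HIV share of the labelled-infected group is 6.9% to 15.6% against 10% in the cohort; neither direction nor size can be fixed from the protocol. The resulting bias in an outcome ratio is probably modest: about 0.97 to 1.06 if maternal HIV doubles the risk.

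Only the observational infected-versus-uninfected contrast is affected, for outcomes not restricted to children of HIV-positive mothers. It is worth correcting because the remedy works whichever way the imbalance runs.

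**What to change.** 1. In Appendix 4, add maternal HIV status to the adjustment for the infected-versus-uninfected schistosomiasis comparison, or stratify that comparison by it. HIV serology is already done at enrolment, so this needs no new data. It removes confounding by HIV mix; it does not remove misclassification of infection within each HIV group.
2. As a secondary step, state whether an antigen-positive, stool-negative woman counts as infected, and report the contrast under both definitions (stool only; stool or antigen) as a sensitivity analysis. Making stool alone the sole definition is not clearly better, since the protocol calls stool insensitive in HIV-infected women.

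The cost is wording and one additional analysis.

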# Haematology

- Full blood counts and eosinophil counts will be performed in the MRC microbiology laboratory using an automated Coulter counter. When eosinophil counts cannot be performed using the automated method they will be done using a thin film stained with Leishman's stain, and calculated from a differential white cell count.
- CD4+ T cell counts will be performed using a FACScount instrument in the MRC microbiology laboratory.
- The laboratory subscribes to the British National External Quality Assessment Scheme for quality assurance for CD4+ T cell counts.

# Special diagnostic procedures in children

Clinical diagnoses will be made for acute lower respiratory infections and diarrhoea, as described below (Outcome (3)); malaria will be defined using clinical criteria and parasite density. Special investigations will be used for measles, tuberculosis and HIV infection.

- measles. A serum sample will be obtained 4 weeks after an episode of clinical measles. This will be examined for measles antibody in order to confirm the diagnosis.
- tuberculosis. Samples for microscopy and culture for *Mycobacterium tuberculosis* will be obtained as clinically indicated. Where there is sufficient material a portion will be used for microscopy and a portion will be injected into BACTEC bottles and sent for culture at JCRC. Remaining material will be cultured on LJ medium at UVRI, and a portion will be stored for examination by Ligase Chain Reaction (LCR). Two blood samples (approximately 1 ml) will be obtained, one before treatment and the other after 4 weeks of treatment for examination of the whole blood assay response to the *M. tuberculosis* specific antigen, ESAT-6.
- *HIV infection.* Samples will be obtained from children of HIV-positive mothers for examination at 6 weeks (a filter-paper blood spot for DNA-PCR) and at 18 months (a filter-paper blood spot for DNA-PCR, a serum sample for HIV-antibody testing and a plasma sample for measurement of viral RNA.

# Assessment of TB infection in 5-6 year olds. Protocol amendment, January 2009.

To determine prevalence and incidence of TB infection among five to six year old children in the cohort (approximately 830 children)

- Among five and six year olds, questions will be asked regarding history of TB exposure, disease and treatment.
- **T-spot.TB**® assays will be performed for all five and six year olds. These investigations will allow us to determine the prevalence of T-spot.TB®-positivity at age five and six years and,

hence, to estimate the prevalence of TB infection at age five, and the incidence of TB infection between age five and six years.

- **Tuberculin skin testing (TST) will be performed at age five years plus three weeks** among those who are contacts of a TB patient or T-spot.TB®-positive and among 50 T-spot.TB®-negative controls (expected number, 260 children). TST will be repeated at age six years in this group, excluding those with an initial TST>10mm. This will allow comparison of T-spot.TB® findings with the more conventional TST results.
- Additional blood samples for repeat T-spot.TB® assays (each 5 ml) will be requested at 5 years plus 3 weeks for all children with a history of household contact with a TB patient, or with a positive T-spot.TB® result (expected to be a total of about 210 children) and for the 50 T-spot.TB®-negative controls selected to receive a TST; and at 5 years plus 27 weeks for all children with a history of household contact with a TB patient, or with a positive T-spot.TB® result (approximately 175 children). This will allow the stability/ repeatability of the test result to be determined. In this group of children, additional peptide pools will be added to the assay to determine whether responses to antigens expressed by *Mycobacterium tuberculosis* can be detected if, or when, responses to the standard antigens are lost.

